3.2 Randomisation

Patients with septic shock fulfilling the inclusion criteria will be randomised if they do not fulfil an exclusion criterion. The 1:1 randomisation will be centralised and web-based according to the computer-generated allocation sequence list, stratification variables (haematological or metastatic cancer (Y/N) and trial site), and varying block size at Copenhagen Trial Unit (CTU). The allocation sequence list will exclusively be known to the data manager at CTU and will be unknown to the investigators to allow immediate and concealed allocation to one of the two intervention groups. Each participant will be allocated a unique patient-screening number.

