10.2 Statistical methods

The analyses will be done in the intention-to-treat (ITT) population defined as all randomised participants for whom there is consent for the use of data. We will perform the primary analyses adjusted for the stratification variables [45] and challenge the primary result in analyses adjusted for important baseline risk factors (co-morbidities, higher SMS score, and focus of infection (other foci vs. urinary tract infection)[43, 46] and use of corticosteroids, which may reduce the time in ICU and thus the time exposed to the protocol [47]) and analyses of subgroups (Table 2) and the per-protocol population being the ITT population except those having one or more major protocol violations as defined below (Table 3). If there is more than 5% missing data for outcomes and/or covariates, we will impute the missing data using multiple imputations as described below (10.2.4).

All analyses will be 2-tailed and we will use Fisher's exact test for unadjusted comparisons of dichotomized outcomes (mortality at 90-days and 1-year, SAEs and SARs) and logistic regressions for adjusted analyses of these outcomes. The remaining secondary outcomes are continuous measures; we expect that these are highly skewed (non-normally distribution), because of inflation of specific values such as zero for days alive outside hospital for all patients who die while at the ICU. We will use statistical methods that can accommodate this type of data; the precise models will be specified in the detailed statistical plan.

Several of the secondary outcome measures are composite; we will also analyse each component of these outcomes as recommended [42]; the precise models will be specified in the detailed statistical plan.

Table 2. Heterogeneity of the intervention effects on the primary outcome will be analysed in the following subgroups based on baseline characteristics

Subgroup	Definition	Expected direction of	Statistical test
		the interaction	
Participants who are mechanically ventilated	Invasive mechanically ventilated (yes/no)	Larger effect of fluid restriction in mechanically ventilated participants	Test of interaction in the adjusted analysis described above; P- value 0.01

The CLASSIC trial protocol Page 32/82

Participants with	KDIGO (creatinine)	Larger effect of fluid	Test of interaction in
severe acute kidney	criteria of 2 or above	restriction in acute	the adjusted analysis
injury	[41] (yes/no)	kidney injury	described above; P-
			value 0.01

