In any multiple imputation, we will use all relevant outcomes and the stratification variables (site and metastatic or hematologic cancer), SMS-ICU¹⁴ at baseline, site of infection at baseline, comorbidities at baseline (ischemic heart disease or heart failure, chronic hypertension or chronic RRT), use of corticosteroids at baseline, mechanical ventilation at baseline, highest p-creatinine 24 hours prior to randomisation, habitual p-creatinine, p-lactate at baseline, participant weight at baseline, and volume of IV fluids given prior to randomisation. Multiple imputation will be performed separately in the two intervention groups before pooling the full dataset, and the primary result of the trial will be based on these data. The unadjusted, non-imputed analysis will also be presented. If multiple imputation is used, we will also include a best-worst worst-best case scenario to assess the potential impact of any pattern of missingness including that data are 'missing not at random' (MNAR criterion). In the 'best-worst-case' scenario it is assumed that all participants lost to followup in the experimental group e.g. have survived; and that all patients with missing outcomes in the control group have not survived. Conversely, in the 'worst-best-case' scenario, it is assumed that all participants who were lost to follow up in the experimental group have had a harmful outcome; and that all those lost to follow-up in the control group have had a beneficial outcome. When continuous outcomes are used, a 'beneficial outcome' will be defined as the group mean plus two

standard deviations (SD) of the group mean or highest possible value whichever is smallest, and a 'harmful outcome' will be defined as the group mean minus two SD of the group mean or lowest possible value whichever is highest.

General analytical principles

The analyses will be done in the intention-to-treat (ITT) population defined as all randomised participants for whom there is consent for the use of data. The conclusion of the trial will be based on the ITT analysis.

The per-protocol population is defined as the ITT population except those having one or more major protocol violations.

Statistical analyses

Primary outcome

Four analyses will be performed for the primary outcome:

Primary analysis:

1. Logistic regression analysis adjusted for the stratification variables¹⁵ (site and hematologic malignancy /metastatic cancer) in the ITT population. P-values will be two-tailed

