Sensitivity analyses:

A two-tailed logistic regression analysis adjusted for the stratification variables, the SMS-ICU¹⁴ focus of infection (other foci versus urinary tract infection)^{14,16} and use of corticosteroids¹⁷
 A two-tailed logistic regression analysis in the per-protocol population adjusted for the stratification variables

4. Two-tailed logistic regression analyses in the pre-planned subgroups adjusted for the stratification variables

We will report absolute and relative risk ratios with 95% CIs for the primary analysis of the primary outcome (analysis 1) (P-value <0.05), computed using glm-models with appropriate link functions and binomial error-distribution. Further, we will report the crude event rates in each group and a Kaplan-Meier survival curve for the crude data of the primary outcome.

Secondary outcomes

Dichotomous secondary outcomes will be analysed in the same way as the primary analysis for the primary outcome, i.e.:

• SAEs

Two-tailed logistic regression adjusted for the stratification variables in the ITT population

- SARs
 Two-tailed logistic regression adjusted for the stratification variables in the ITT population
- 1-year mortality

Two-tailed logistic regression adjusted for the stratification variables in the ITT population

A Kaplan-Meier survival curve will be reported for the crude data for secondary outcome 1-year mortality.

The remaining secondary outcomes are continuous measures which we expect to be skewed (nonnormally distributed), because of inflation of specific values such as zero for 'days alive outside hospital' for all patients who die while in the ICU. The outcome measures will be analysed as follows:

- Days alive at day 90 without life support
 Generalised linear model or nonparametric test stratified for site in the ITT population
- Days alive and out of hospital at day 90
 Generalised linear model or nonparametric test stratified for site in the ITT population
- HRQoL 1-year after randomisation⁸
 Generalised linear model or nonparametric test stratified for site in the ITT population
- Cognitive function 1-year after randomisation⁹

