Generalised linear model or nonparametric test stratified for site in the ITT population For the generalised linear model we will initially use Poisson distribution, alternatively negative binomial.¹⁸ If the assumptions for Poisson distribution or negative binomial distribution are not met, data will be analysed using the nonparametric Van Elteren test adjusted for site, but no other variables.¹⁹

The following secondary outcome measures are composite; SAEs, SARs, days alive at day 90 without life support. We will report each component of these outcomes in an appendix to the primary publication without P-values due to the lack of adjustment for multiple comparisons. We will report absolute and relative risk ratios with 99% CIs for dichotomous secondary outcomes. For continuous secondary outcomes we will report mean differences with 99% CIs if they are normally distributed and medians with 99% percentile-based bootstrapped CIs for non-normally distributed continuous secondary outcomes (P-value 0.01) due to the multiplicity of these. A detailed definition of the level of significance for the secondary outcomes is available in the supplement to the published statistical analysis plan. ¹

Sample size

Primary outcome

We plan to enrol 1554 (2 x 777) patients to be able to show a 15% relative risk-reduction (RRR) (7% absolute) in the restrictive group on the primary outcome from an estimated 45% 90-day mortality in the standard care group at type 1 and 2 error levels of 5% and 20% respectively, corresponding to a number needed to treat (NNT) of 14 or less. The anticipated relative risk reduction of mortality and the estimated mortality in the control group is based on data from previous RCTs and systematic reviews.^{20–24}

Trial sequential analysis of existing trials (n=8) have shown that less than 15% of the required information size of 3956 patients to detect or reject a 15% RRR in all-cause mortality with lower versus higher fluid volumes has been reached.²⁵

Secondary outcomes

We expect to have the following statistical power for the secondary outcomes based on 2 x 777 participants, a type 1 error level of 1% and a RRR of 15% in the fluid restriction group versus standard care group:

- 50% power for the number of participants with one or more SAEs (control event rate 25% ^{21,22})
- 10% power for the number of participants with one or more SARs (control event rate 5%^{21,22})

- 80% power for the mortality at 1-year (control event rate 55%^{21,22})

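### The SAP names only site as stratifier for the four continuous secondary outcomes, and does not explain why the other randomisation stratum, cancer, is left out

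*SAP*

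**What the plan says.** Protocol section 3.2 allocates participants using "stratification variables (haematological or metastatic cancer (Y/N) and trial site), and varying block size". Section 10.2 states: "We will perform the primary analyses adjusted for the stratification variables". For the skewed continuous outcomes the same section adds: "We will use statistical methods that can accommodate this type of data; the precise models will be specified in the detailed statistical plan".

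In the SAP, the primary analysis of 90-day mortality is "Logistic regression analysis adjusted for the stratification variables", with site and cancer both named. For SAEs, SARs and 1-year mortality: "Dichotomous secondary outcomes will be analysed in the same way as the primary analysis for the primary outcome".

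For days alive without life support, days alive and out of hospital, HRQoL and cognitive function, each entry reads "Generalised linear model or nonparametric test stratified for site in the ITT population". The SAP starts with a Poisson model and moves to a negative binomial. "If the assumptions for Poisson distribution or negative binomial distribution are not met", then "data will be analysed using the nonparametric Van Elteren test adjusted for site, but no other variables". The threshold for these outcomes is P 0.01.

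**The concern.** When allocation is blocked within a prognostic factor, the arms are balanced on it by design. An analysis that ignores the factor uses a variance that still includes the between-stratum variation the blocking has removed. The standard error is then slightly too large and the test conservative. The plan accepts this principle: both documents support adjustment by citing a paper on the improper analysis of trials randomised in stratified blocks.

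Cancer is not a trivial factor here. In the SMS-ICU table (Protocol Appendix 6) it carries 7 points, the largest weight of any yes/no item. Death bears on all four outcomes: two count days alive, and Protocol Appendix 2 gives non-survivors the worst score on the other two.

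At stake are consistency and calibration for four of the seven secondary outcomes. A reader will ask why they follow a different adjustment rule from the rest and will find no answer in the SAP.

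**Working it through.** **1. The texts side by side**

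| Outcome | Analysis | Stratifiers named |
|---|---|---|
| 90-day mortality | logistic regression | site and cancer |
| SAEs, SARs, 1-year mortality | logistic regression | site and cancer |
| Four continuous outcomes | Poisson, then negative binomial | unclear; only site appears |
| Same, if count-model assumptions fail | Van Elteren | site; all else excluded |

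The entry for the continuous outcomes can be read two ways: the words about site may qualify the nonparametric test alone or the generalised linear model as well. Either way, cancer is not named.

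**2. Is the fallback likely to be used?** Plausibly. The SAP itself expects inflation at values such as zero, and Protocol Appendix 2 converts EQ-5D-5L to an index, which is not a count.

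**3. Expected size of the effect.** The documents give no figure that depends on this choice, so there is none to reproduce. Inputs:

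- SMS-ICU table: 24 points predicts 46.7% 90-day mortality and 31 points (7 more) predicts 69.4%, a difference of 0.227.
- Cancer share p: not given; assumed 10 to 20%.
- Share of variance in death explained by cancer: R² = p(1−p)d² / [m(1−m)], where d is the risk difference and m the overall risk.

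Results:

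- p = 0.10: m = 0.467 + 0.10 × 0.227 = 0.4897; R² = 0.00464 / 0.2499 = 1.9%.
- p = 0.20: m = 0.467 + 0.20 × 0.227 = 0.5124; R² = 0.00824 / 0.2498 = 3.3%.

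Rounded, this is 2 to 3.5%. With near-complete balance on cancer, the SD of the site-only test statistic under the null is about √(1−R²), and the true two-sided size at nominal 1% is 2[1 − Φ(2.576/SD)]:

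- R² = 2%: SD = 0.990; 2.576/0.990 = 2.602; size 0.93%.
- R² = 3.5%: SD = 0.982; 2.576/0.982 = 2.622; size 0.87%.

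**4. Simulation.** Assumptions: n = 1554, 30 sites, blocks of 4, 6 or 8 within site by cancer, overall mortality 45%, zero-inflated days-alive outcome, two-sided 1% level. Power is for a 7-point mortality difference.

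| Cancer share / mortality with cancer | Null rejection: site | Null rejection: site × cancer | Power: site | Power: site × cancer |
|---|---|---|---|---|
| 10% / 65% | 1.16% | 1.20% | 42.2% | 42.8% |
| 20% / 65% | 0.76% | 1.12% | 40.2% | 40.8% |
| 30% / 65% | 1.04% | 1.52% | 42.8% | 43.5% |
| 20% / 75% | 0.80% | 0.96% | 41.5% | 41.2% |

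The Monte Carlo standard error is about 0.2 percentage points for null rejection (2500 trials) and 1.4 for power (1200 trials). These runs are too small to fix the size of the effect, but they show no inflation with site only and no material power difference.

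Larger runs (6000 trials per scenario; 20, 30 or 45 sites; cancer share 10 to 20%) gave a smaller SD of the test statistic for site only in every null scenario. Under strong cancer prognosis, rejection was about 0.78% (site) against 1.04% (site × cancer), with standard error √(0.01 × 0.99/6000) = 0.13 percentage points. Under weaker prognosis there was no clear difference. Crossing gave equal or slightly lower power (for example 37.9% against 38.4%) and dropped about 1 to 13 participants in one-arm cells.

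**The case against.** The strongest defence is that the choice is explicit and pre-specified. The SAP says outright that nothing but site enters the fallback test, and it cites a methods paper for analysing count data. The Van Elteren test applies only after two count models have been rejected. Avoiding sparse strata is a plausible motive. The error runs in the safe direction, touches secondary outcomes only, and leaves untouched the primary model, which includes cancer. All of this stands, though the SAP never states the sparse-strata motive.

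A reader might infer that the SAP breaks a protocol rule to adjust for both factors. The documents do not support that. The sentence in section 10.2 speaks of the primary analyses, which can mean the main analysis of every outcome or the analysis of the primary outcome alone. The same section hands the models for exactly these outcomes to the SAP.

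A reader might also infer that all four outcomes will certainly be analysed by site alone. That goes too far as well, because the covariates of the count models are not stated.

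The defence does not remove the inconsistency. The Van Elteren test accepts any strata, including site-by-cancer cells, so excluding cancer is not a technical necessity. The summary of changes to the SAP does not take the point up.

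**Conclusion.** The point holds as a minor, unexplained inconsistency. Four of seven secondary outcomes name one of the two blocking factors, while every other outcome in the SAP is adjusted for both.

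The consequence is slight conservatism in the fallback test: a true size of about 0.8 to 1.0% at nominal 1%. That range rests on an assumed cancer share (10 to 20%), an assumed prognostic strength and 20 to 45 assumed sites; none of these is given for the enrolled population. A seriously mis-calibrated test should not be inferred: with weaker prognosis the simulations cannot separate the two analyses. There is no false-positive inflation, no material power change and no bearing on the primary conclusion. The case for change is agreement with the design and within the SAP.

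**What to change.** - State the covariates of the Poisson and negative binomial models, and include cancer alongside site.
- For the rank-based fallback, use site and cancer as strata. Pool sparse or one-arm cells with the other cancer category at the same site, by a rule that does not look at outcomes. A rank-based model with both terms would also serve.
- If site-only stratification is kept, give the reason.

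The cost is a line or two of SAP text and one re-run. Without pooling, the full crossing loses about 1 to 13 of 1554 participants from the test and can cost about 0 to 1 percentage point of power; pooling is meant to avoid this. The SAP's summary of changes dates the final analyses to March 2022, so the result should be shown as a labelled supplementary analysis beside the pre-specified one, not in its place.

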7.2 Secondary outcomes

- Number of participants with one or more serious adverse events (SAEs) in the ICU defined as ischaemic events (cerebral, cardiac, intestinal or limb ischaemia) or as a new episode of severe acute kidney injury (modified KDIGO3 [41])
- Number of participants with one or more serious adverse reactions (SARs) to IV crystalloids in the ICU as defined in section 8.2
- Days alive at day 90 without life support (vasopressor / inotropic support, invasive mechanical ventilation or renal replacement therapy)
- Days alive and out of hospital at day 90
- All-cause mortality at 1-year after randomisation
- HRQoL 1-year after randomisation measured using the EuroQoL (EQ)-5D-5L and EQ-VAS scores. Participants who have died will be assigned the lowest possible scores
- Cognitive function 1-year after randomisation as assessed by the Montreal Cognitive Assessment (MoCa) score

Several of the secondary outcomes above are composite outcomes. The single components of these will also be analysed and presented in a supplement to the primary publication.

8 Safety

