The trial intervention is not blinded for investigators, clinical staff and patients, as blinding of IV fluid restriction versus standard care is not feasible. The statistician assessing all outcomes will be masked for the allocation. The data for 90-day and 1-year mortality will be collected from electronic patient records or central national registries in most participating countries. The remaining outcomes will be provided by local investigators, who are not blinded for the intervention, by entering data from patients' files. The management committee will write the preliminary abstract with the group allocation masked; this abstract will be published as a supplement to the primary trial report.^{5,6}

Outcome measures

Primary outcome measure

The primary outcome measure is all-cause mortality at day 90 after randomisation.

Secondary outcome measures

We have 7 secondary outcome measures:

 Number of participants with one or more serious adverse events (SAEs) in the ICU defined as ischaemic events (cerebral, cardiac, intestinal or limb ischaemia) or a new episode of severe AKI (modified KDIGO3⁷)

- Number of participants with one or more serious adverse reactions (SARs) to IV crystalloids in the ICU
- Days alive at day 90 without life support (vasopressor / inotropic support, invasive mechanical ventilation or renal replacement therapy (RRT))
- Days alive and out of hospital until day 90
- All-cause mortality at 1 year after randomisation
- Health-related quality of life (HRQoL) 1 year after randomisation measured using the EuroQoL EQ-5D-5L scores ⁸
- Cognitive function 1 year after randomisation as assessed by the telephone MINI-Montreal Cognitive Assessment (MINI-MoCA) score ⁹

Detailed definitions of the outcome measures are available in the protocol.

Missing data

If less than 5% of data required for any specific analysis on primary or secondary outcomes are missing, a complete case analysis will be performed. If more than 5% are missing, and it is concluded that data are not 'missing completely at random' (MCAR criterion),^{10,11} multiple imputation using chained equations will be performed by creating 25 input datasets under the assumption that the data are 'missing at random' (MAR criterion).^{12,13}

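### For 1-year HRQoL and cognition, with death scored as worst, the median prescribed for non-normal data mostly shows whether an arm's deaths pass half, and it matches neither planned test

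*SAP*

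**What the plan says.** **Scoring of deaths.** Protocol section 7.2 states for HRQoL: "Participants who have died will be assigned the lowest possible scores". Appendix 2 gives the same rule for HRQoL and for the MoCA score. The SAP refers to the protocol for outcome definitions and analyses all randomised participants with consent, so the dead are in the sample.

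**Test.** Under Secondary outcomes in Statistical analyses, the SAP starts with a Poisson or negative binomial generalised linear model. Then: "If the assumptions for Poisson distribution or negative binomial distribution are not met, data will be analysed using the nonparametric Van Elteren test".

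**Estimate.** This is chosen by a different criterion, normality: "mean differences with 99% CIs if they are normally distributed", otherwise "medians with 99% percentile-based bootstrapped CIs for non-normally distributed continuous secondary outcomes". The SAP's sample size section expects HRQoL and cognition to be highly skewed, so the median branch is the one it foresees. The text does not say whether the interval is for each arm's median or for the difference.

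**Awareness of the floor.** Protocol section 10.2 promises: "We will use statistical methods that can accommodate this type of data". The SAP explains that skew is expected "because of inflation of specific values such as zero". The March 2022 changes to the SAP do not touch this point.

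**The concern.** A median ignores how far values lie from the middle. When one value, here the score for death, holds about half of an arm, the median is decided by whether that share is just above or just below 50%. Above half, it is the floor however well survivors do. Just below half, it jumps to the score of the worst-off survivors. The planning mortality at 1 year puts the two arms on either side of that point.

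The planned tests do use the whole distribution, but neither compares medians. The estimate printed next to the P-value for two of the seven secondary outcomes may therefore carry almost no information on HRQoL or cognition, or may suggest a large contrast where the underlying shift is modest.

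**Working it through.** **Inputs.** 777 patients per arm and 1-year control mortality of 55% (Protocol 10.1.2; SAP, Sample size). A 15% relative risk reduction (RRR) gives 0.85 × 55% = 46.75% in the restrictive arm; this figure is derived, not printed.

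**The plan's own figure.** The plan states 80% power for this mortality contrast at a two-sided 1% level. The pooled normal formula gives: difference 0.0825; null SE √(2 × 0.50875 × 0.49125/777) = 0.02536; alternative SE √((0.55 × 0.45 + 0.4675 × 0.5325)/777) = 0.02528; z = (0.0825 − 2.576 × 0.02536)/0.02528 = 0.68; power 75%. The 80% is not reproduced, but nothing below depends on it.

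**Step 1: when is the median the death score?** With 777 values the median is the 389th, so it is the floor if at least 389 patients died. The chance is q(p) = P(Bin(777, p) ≥ 389):

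| True mortality | Chance that the median is the floor |
|---|---|
| 55% | 99.7% |
| 52.25% | 90% |
| 49.5% | 39% |
| 46.75% | 3.5% |
| 45% | 0.3% |

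**Step 2: where is the restrictive median?** (0.50 − 0.4675)/0.5325 = 0.061, about the 6th percentile of survivors. In counts: about 363 deaths, so rank 389 − 363 = 26 of 414 survivors.

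**Step 3: both arms together.** With independent arms, the medians lie on opposite sides of the floor with probability qc(1 − qr) + qr(1 − qc), and both are the floor with probability qc·qr:

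| Control mortality, RRR | Opposite sides | Both floor |
|---|---|---|
| 55%, 15% | 96% | 3.5% |
| 55%, 10% | 61% | 39% |
| 55%, 5% | 11% | 89% |
| 55%, 0% | 0.5% | 99.5% |
| 60%, 15% | 29% | 71% |
| 45%, 15% | 0.3% | about 0% |

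In the last row both medians are survivor scores in almost every trial. In the first row, part of the contrast reflects a real mortality difference of about 8 points.

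**Step 4: the per-arm interval.** The 99% order-statistic ranks for a median of 777 values are 353 and 425. At 55% mortality the interval has zero width at the floor in 58% of trials, and in 42% it holds both the floor and survivor scores. At 46.75% it holds both in 78%.

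**Step 5: benefit in survivors only.** Let 55% die in both arms and let restrictive survivors score better by 10% of the scale. From q(0.55)², both medians are the floor in over 99% of trials. In simulations with 30 equal sites and five assumed survivor distributions, Van Elteren gave P < 0.01 in 18–66% of the same trials. The size of the gain and the distributions are assumptions; the floor result is not.

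**Step 6: non-response.** Deaths are always scored, so complete-case analysis drops only survivors. Below 5% missing, the SAP rule is that for "any specific analysis on primary or secondary outcomes are missing, a complete case analysis will be performed". If 10% of survivors do not respond, the missing share is 0.10 × (0.5325 + 0.45)/2 = 4.9%, just under the limit. The share of dead among those analysed becomes 0.4675/(0.4675 + 0.5325 × 0.9) = 49.4% and 0.55/(0.55 + 0.45 × 0.9) = 57.6%. Opposite sides then falls from 96% to about 63%, and both floor rises to about 37%.

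**Step 7: a measure matched to the rank test.** Take the probability that a restrictive patient does better than a control patient, plus half the ties. With equal survivor scores at 15% RRR: 0.5325 × 0.55 + ½ × 0.4675 × 0.55 + ½ × 0.5325 × 0.45 = 0.541. At 10% RRR: 0.505 × 0.55 + ½ × 0.495 × 0.55 + ½ × 0.505 × 0.45 = 0.528. It changes gradually where the median flips.

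**The case against.** - **It is only a summary.** If the medians are read as one per arm, they are description beside a valid rank test, which is a common pairing, and 1-year mortality with its Kaplan-Meier curve lets a reader understand a floor value. This stands as far as it goes. But mortality gives no effect size for HRQoL or cognition, and the plan names no other estimate in the branch it expects to use.
- **The SAP does name another estimate.** A reader might infer that the median is the only estimate in the SAP. It is not: a mean difference is named for normal data. With about half the values at one score, that branch cannot apply.
- **The interval would contradict the P-value.** A reader might infer a rate at which the two disagree. That needs the interval to be for a difference in medians, which the SAP does not state, so no such rate is claimed.
- **The model branch is unlikely.** Data with about half the values at the floor would probably fail the Poisson and negative binomial assumptions and go to Van Elteren. This is fair; the main mismatch is median against ranks.
- **Mortality may be lower.** Pilot 90-day mortality was 33% and 41% (Protocol, Table 1). At 45% or less in both arms the median is a survivor score and responds to survivor status. But 55% is the plan's own 1-year planning value, and a pre-specified estimate should work there.

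**Conclusion.** The point holds as a defect in the reported estimate for two secondary outcomes. At the plan's own mortality the control median is almost surely the death score, and at a 10% RRR chance decides between two quite different pictures, 61% to 39%. A benefit confined to survivors can give P < 0.01 beside two identical floor medians.

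The floor figures rest on 777 evaluable patients per arm, independent arms, mortality near the planning values, and no survivor at the worst score; any survivor there would make a floor median more likely. Only Step 5's test rates depend on assumed survivor scores.

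A reader might infer that the tests are invalid or that the trial's conclusion is at risk. The documents do not support that: the test at the 1% level, 1-year mortality and the primary outcome are untouched. The correction is worth making because it is cheap, but the stakes are modest.

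**What to change.** In the SAP's Secondary outcomes section, for HRQoL and MoCA only:

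1. Report with a 99% CI the effect measure that matches the test used. If Van Elteren is used, this is the site-stratified probability of a better outcome. If the generalised linear model is used, it is the mean ratio or mean difference from that model.
2. Keep medians as per-arm description only, and say so.
3. Show survivor scores descriptively beside 1-year mortality.

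The cost is SAP wording and a few lines of code; no new data are needed, and the test and its 1% level do not change. One drawback remains: any single summary that scores death as worst mixes mortality with survivor status. Item 3 is therefore needed, and the survivor comparison must stay descriptive because survivors are not a randomised subset.
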